#### **5.0 Number of Subjects**

This study will enroll a minimum of 10 subjects. We expect an approximate 10% drop-out rate, so we will expect to recruit approximately 12 subjects; and the first 10 to be eligible and complete the study will be used for data analysis. All subjects will receive the study drug, Restasis (cyclosporine ophthalmic solution 0.05%).

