Slit-lamp Examination	The participant's front portion of each eye and contact lenses will be examined with a lighted microscope. The participant will be asked to place his/her chin on the chinrest and place his/her forehead against the bar and look straight ahead. The instrument's light will be shined onto the eye to visualize the ocular surface for approximately 2-3 minutes per eye.
Sodium Fluorescein/Lissamine Green	Sodium fluorescein/Lissamine Green staining will be used to evaluate ocular surface damage indicated by cell damage or death and for assessing an open vs closed PROSE device system. Corneal and conjunctival staining will be scored using the NEI Grading System.
R-Scan	Non-invasive imaging modality with automated classification of ocular redness level. Instrument used: OCULUS Keratograph 5M. The participant will be asked to place his/her chin on the chinrest and place his/her forehead against the bar and look straight ahead. The investigator will perform a scan of the eye to obtain an image of the front surface of the eye. The computer will then use an embedded software algorithm to quantify the level of redness on a scale from 0 to 4 in 0.1 increments.
Questionnaires	Subjects will be asked to fill out the following questionnaires: 
 
• Ocular Surface Disease Index (OSDI)
 
• Restasis Tolerability Questionnaire
 

*Figure 2. Table including descriptions of tests*

Statistical Analysis:

Subject data will be compared to their baseline status prior to initiating usage of the study drug. Subjects will be reevaluated at 1 week and 1 month visits and the data will be evaluated and compared to baseline. This is a small preliminary pilot study to evaluate tolerability of this treatment model utilizing Restasis. Given the small number of subjects and given our question of initial tolerability, the predominant nature of the results are observational and meant to provide an early means of addressing the question of tolerability.

The following data will be collected. They are all minimal to no risk.

- Visual acuity
  - Visual acuity will be measured on a Snellen chart and converted to logMAR values
- Tolerability survey
  - The Tolerability Questionnaire involves the subject answer a series of questions to assess their symptoms.
- Ocular Surface Disease Index (OSDI)

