  - The Ocular Surface Disease Index is a validated questionnaire consisting of a group of 12 questions designed to assess symptoms of ocular surface disease. The questionnaire is administered by a trained medical staff member. All questions are answered on a scale of 0 to 4 (or the subject has an option to not answer a question). The end score is then mathematically converted to a 0-100 scale, with 0 being no symptoms and 100 being the most severe symptom score.
- Corneal staining (NEI Grading System)
  - Corneal staining is a routine ophthalmic and optometric test which utilizes Sodium Fluorescein stain on the eye to evaluate the health of the ocular surface. The amount of stain adherent to the ocular surface is then recorded utilizing standardized scales. It is minimal risk, including risk of irritation, redness, burning and stinging.
  - The NEI Grading System is a standardized method for quantifying the level of ocular surface signs noted on slit lamp examination. The scale ranges, in whole numbers, from 0 to 3, in 5 distinct sections on the cornea, with 0 indicating that the particular sign is not present and 3 being the most severe version of that specific sign (ie corneal staining, conjunctival staining, conjunctival redness) being measured. The overall score for one eye's cornea (5 sections on each cornea) ranges from 0 to 15.
- Conjunctival staining (NEI Grading System)
  - Conjunctival staining is a routine ophthalmic and optometric test which utilizes Lissamine Green stain on the eye to evaluate the health of the ocular surface. The amount of stain adherent to the ocular surface is then recorded utilizing standardized scales. It is minimal risk, including risk of irritation, redness, burning and stinging.
  - The NEI Grading System is a standardized method for quantifying the level of ocular surface signs noted on slit lamp examination. The scale ranges, in whole numbers, from 0 to 3, in 6 distinct sections on the cornea, with 0 indicating that the particular sign is not present and 3 being the most severe version of that

specific sign (ie corneal staining, conjunctival staining, conjunctival redness) being measured. The overall score for one eye's conjunctiva (6 sections on each eye's conjunctiva) ranges from 0 to 18.

- Conjunctival Redness (Efron and modified Efron scale)
  - Conjunctival redness involves the visual inspection of the ocular surface by the investigator and grading of the amount of redness on a standardized scale.

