  - The Efron Grading Scales for Contact Lens Complications is a standardized method for quantifying the level of ocular surface signs noted on slit lamp examination. The scale ranges, in whole numbers, from 0 to 4, with 0 indicating that the particular sign is not present and 4 being the most severe version of that specific sign (ie corneal staining, conjunctival staining, conjunctival redness) being measured.
- Oculus Keratograph 5M R-Scan value
  - This device is a non-invasive imaging modality which takes an image of the front surface of the eye and through the use of a computerized algorithm categorizes the level of redness automatically on a continuous scale that increases in increments of 0.1 starting from 0 up to 4.
  - The investigator will image the ocular surface utilizing the Oculus Keratograph 5M device. The computer will then use an embedded software algorithm to quantify the level of redness on a scale from 0 to 4 in 0.1 increments, with 0 being no redness and 4 being the most severe redness level.

Findings for all endpoints will evaluated to measure subjective and objective differences in clinical signs and symptoms.

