**Novel Use of Cyclosporine Ophthalmic Emulsion 0.05% in a PROSE Device**

**NCT#: NCT04918823**

**Version: 8/27/2024**

## Statistical Analysis

Statistical analysis was performed using Visual Studio Code (Microsoft Corp., Redmond WA) with python version 3.9.12. Subject data post-treatment was compared to their baseline data, collected prior to initiating use of the study drug. For Group A, the data collected at Visit 1A was considered to be their baseline data pre-intervention. For Group B, the data collected at Visit 1B was considered to be their baseline data (post-initiation of Purilens and pre-initiation of cyclosporine). The core algorithm used was based on statistical functions module `scipy.stats`. For univariate data analysis (before/after visits), paired t-test was performed since every patient received treatment. Paired t-test was conducted by `scipy.stats.ttest_rel` and <https://www.statskingdom.com/paired-t-test-calculator.html>. For bi-variate data, two-way ANOVA (Analysis of variance) was performed. Two-way ANOVA was conducted by `sm.stats.anova_lm(model)` function. The significance level was set to a P-value of  $\leq 0.05$  in all instances of analysis.

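### Nothing keeps the R-scan score from the clinician who grades redness afterwards, so the Efron grade may be anchored to it; whole-grade scoring also costs some precision (minor)

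*Protocol*

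**What the plan says.** Protocol Section 8.0 lists the steps of each visit in order. The R-scans with and without the lens are steps f and h at Visit 1A, d and f at Visit 1B, and e and g at Visits 2 and 3. The slit-lamp examination that contains the Efron and modified Efron grades follows each time (steps i, g, h and h). The duration table for Visit 1B in Section 10.0 lists the slit lamp above the R-scan, but that table gives minutes per procedure, not a sequence.

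On who does what, Section 10.0 says of the R-scan: "The investigator will perform a scan of the eye to obtain an image of the front surface of the eye". It describes conjunctival redness as "visual inspection of the ocular surface by the investigator and grading of the amount of redness on a standardized scale". No passage masks the grader to the automated score.

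On resolution, the Efron entry reads "The scale ranges, in whole numbers, from 0 to 4", while the R-scan software is to "quantify the level of redness on a scale from 0 to 4 in 0.1 increments". The modified Efron scale is named at every visit and in Section 9.0, but its steps are not given.

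On analysis, Section 5.0 states that "the first 10 to be eligible and complete the study will be used for data analysis". For before/after data the SAP says "paired t-test was performed since every patient received treatment", with the threshold at 0.05. Protocol Section 23.0 also allows signed-rank tests.

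**The concern.** Section 12.0 presents the R-scan as an objective reading, set against a clinician's subjective grade. That contrast is informative only if the clinician grades without sight of the score. A grader who has just seen a numeric redness value on the same 0-4 range may move towards it. If both readings then fall, or both rise, the Efron result may partly repeat the R-scan. Redness also bears on safety: Section 12.0 quotes conjunctival hyperemia among the drug's reported reactions, so a clinician's own impression of worsening is worth protecting.

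The lesser concern is that a five-value score hides small changes, in either direction, in a comparison of 10 subjects.

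**Working it through.** **Order and access.** Four facts stand together: scan before grade at all four visits (Section 8.0); the same role name for both tasks (Section 10.0); no masking statement; and a rationale that rests on the contrast between the two methods (Section 12.0). They show that the score can be known when the grade is chosen. They do not show that it is. No arithmetic applies, and the documents give nothing from which to size the bias.

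**The plan's own figure.** 10 / (1 − 0.10) = 11.1, rounded up to 12, so the recruitment figure in Section 5.0 reproduces. No SD, target change or power is given for redness. Everything below uses n = 10, a two-sided 0.05 level (sidedness is not stated) and assumed SDs.

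**Detectable change.** Rounding to a step s adds about s²/12 variance per reading, hence s²/6 per before/after difference: 0.167 for whole grades, 0.042 for half grades, 0.002 for 0.1 steps. With n = 10, the paired t-test has 80% power at 0.996 SD of change. Detectable mean change = 0.996 × √(SD² + s²/6):

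| Assumed SD of change | Whole grades | Half grades | 0.1 steps |
|---|---|---|---|
| 0.3 | 0.50 | 0.36 | 0.30 |
| 0.5 | 0.64 | 0.54 | 0.50 |
| 0.7 | 0.81 | 0.73 | 0.70 |
| 1.0 | 1.08 | 1.02 | 1.00 |

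For example, at SD 0.5 in whole grades: 0.996 × √(0.25 + 0.167) = 0.64. Whole grades cost 0.20 grade at SD 0.3 and 0.08 at SD 1.0, relative to 0.1 steps.

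**Power for a true 0.3-grade fall.** Simulation, 40,000 runs per row; baseline uniform from 1 to 3; one reading per subject and visit; grader noise the same for every step size:

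| True-change SD | Noise SD per reading | Whole | Half | 0.1 |
|---|---|---|---|---|
| 0.3 | 0.15 | 31% | 49% | 63% |
| 0.3 | 0.25 | 27% | 37% | 44% |
| 0.4 | 0.20 | 25% | 35% | 41% |
| 0.4 | 0.35 | 19% | 24% | 27% |

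**Larger changes.** A second simulation (baseline mean 2, SD 0.7; SD of change 0.3 to 1.0) gives 71-100% power for a true one-grade change in whole grades, against 79-100% in 0.1 steps. For a half-grade change at SD 0.5, whole grades give 57% and 0.1 steps 80%. Averaging two eyes, which itself creates half-grade steps, raises the 57% to 71% (noise correlation between eyes assumed to be 0.7).

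**False positives.** With no true change, the t-test on whole grades rejects in 2-5% of runs, so the error rate is not inflated.

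**A worked pattern.** Four of 10 subjects fall one grade and six are unchanged. The mean is −0.4, the SD is √(10 × 0.4 × 0.6 / 9) = 0.516 and t = −0.4 / (0.516/√10) = −2.45, so P = 0.037. The exact sign-flip P is 2 × 0.5⁴ = 0.125.

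**The case against.** A reader might infer that one person runs the scan, reads the score and then grades. The documents do not say so. The shared role name is the only link, Section 26.0 refers to several investigators, and nothing says the score is displayed before grading. A reader might also conclude that the two endpoints are dependent. That is a possibility, not a documented fact, and neither Section 23.0 nor the SAP plans an analysis that relies on their agreement. These objections stand, and they limit the point to what cannot be excluded.

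On resolution, it is tempting to say that clinician redness is recorded only in whole grades and is too coarse for this study. The whole-number sentence covers Efron; the modified Efron scale may be finer, and its steps are simply unstated. The R-scan already supplies 0.1-step redness. Sample size is the main limit: even 0.1 steps leave power at 27-63% for a 0.3-grade fall. That fall is an illustrative choice, since the documents name no target. The simulations also hold grader noise fixed, while interpolated grades lean more on judgement.

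The P = 0.037 pattern might be read as proof of a resolution defect. It shows instead that the answer depends on the test chosen for a coarse score, and Section 23.0 already allows a signed-rank test.

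What survives is the missing safeguard on order, the unstated modified Efron steps and a modest loss of precision.

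**Conclusion.** The point holds as a minor one. The plan permits the clinician grade to be made with the automated score in view, so the grade may be anchored and cannot be shown to be a separate reading. This follows from the text without any assumed figure, but its size is unknown.

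The resolution point is secondary. Under the assumed SDs, half-grade recording would raise power for a 0.3-grade fall from 19-31% to 24-49%. That is an upper estimate, because extra noise from interpolation is ignored, and the gain shrinks as the SD of change approaches 1. Whether finer steps are valid on a scale that the protocol describes as whole-number cannot be settled from the documents.

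The consequence is limited. Clinician-graded redness is one of seven endpoint types in Section 9.0, the main aim is tolerability and safety, and Section 10.0 calls the results predominantly observational.

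**What to change.** **Main change.** In Section 8.0, at Visits 1A, 1B, 2 and 3, require the Efron and modified Efron grades to be written on the CRF before that visit's R-scan score is opened. Images may still be taken first. The cost is one sentence and one CRF field.

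**Secondary change.** In Section 10.0, state the steps of the modified Efron scale. Record Efron in half-grade or finer interpolated steps from baseline on, and keep the rounded whole grade as the standard score. Whole grades can always be recovered by rounding; finer ones cannot be recovered later. The cost is greater reliance on the grader's judgement and possibly more noise.

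The SAP is written in the past tense. For any readings already taken, the report should state who graded redness and whether the R-scan score was visible at the time.

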## **11.0 Setting**

Subjects will be asked to complete the study visits, which will be conducted in clinical facilities at BostonSight, Needham, MA.

## **12.0 Drugs or Devices**

### **PROSE (Prosthetic Replacement of Ocular Surface Ecosystem):**

The PROSE device is considered a class II medical device by the FDA. All rigid lens materials are FDA approved for use in a rigid contact lens, and they are not investigative devices.

### **RESTASIS (cyclosporine ophthalmic solution 0.05%) (AbbVie Inc.)**

RESTASIS (cyclosporine ophthalmic solution 0.05%) is a topical immunomodulator indicated to increase tear production in patients with ocular surface inflammation associated with keratoconjunctivitis sicca. RESTASIS appears as a translucent homogenous emulsion. The osmolarity is 230 to 320 mOsmol/kg and the pH of the solution is 6.5-8.0. RESTASIS is a FDA approved drug for the increase of tear production in patients with keratoconjunctivitis sicca (dry eye syndrome). FDA approval initially occurred in 1983 and was most recently approved as of October 2003.

The ingredients for RESTASIS are listed below:

- Active Ingredients: Cyclosporine 0.05%
- Inactive Ingredients: Glycerin, castor oil, polysorbate 80, carbomer copolymer type A, purified water, and sodium hydroxide to adjust pH.

"In clinical trials the most common adverse reaction following the use of RESTASIS® was ocular burning (17%). Other reactions reported in 1% to 5% of patients included conjunctival hyperemia, discharge, epiphora, eye pain, foreign body sensation, pruritus, stinging, and visual disturbance (most often blurring)".

#### **Purilens (Lifestyle Inc)**

Purilens is an FDA approved sterile buffered saline solution for cleaning, disinfecting, and storing of contact lenses. It is formulated with sodium chloride and boric acid. Although it is not specifically approved for filling scleral lenses, it is commonly used as off-label for filling scleral lenses and generally accepted as standard of care. Purilens is a pH balanced buffered saline with pH of 7.4, to match the pH of natural human tears.

In our study buffered preservative-free Normal Saline (Purilens) will be used routinely to fill the PROSE reservoir. If a patient is not currently using Purilens to fill the PROSE reservoir they will initiate doing so for two weeks prior to being dispensed the study drug.

**Lissamine Green Ophthalmic Strip (Green Glo, Contacare Ophthalmics and Diagnostics):** An ophthalmic dye used as the gold standard in ophthalmic and optometric practices to evaluate devitalized conjunctival epithelium. Used in the form of a paper strip impregnated with 1.5 mg. of Lissamine Green. The impregnated strip is moistened with one to two drops of sterile normal saline and applied to the inferior conjunctival fornix.

**Flourescein Sodium Strip (Bio Glo, Contacare Ophthalmics and Diagnostics):** An ophthalmic dye used as the gold standard in ophthalmic and optometric practices to evaluate devitalized corneal epithelium. Used in the form of a paper strip impregnated with 1.0 mg. of fluorescein sodium. The impregnated strip is moistened with one to two drops of sterile normal saline and applied to the inferior conjunctival fornix.

#### **Oculus Keratograph 5M (Oculus, Inc)**

The Ocular Keratograph 5M is an FDA cleared ophthalmic device which is exempt from premarket notification requirements. It is an FDA exempt medical device. It is an ophthalmic device used to image the ocular surface. Embedded software algorithms analyze the obtained image to quantify a variety of ocular surface findings. For this study, we will utilize the R-scan function, an automatic classification of redness which quantifies the ocular surface injection (redness). This finding is a surrogate for ocular surface inflammation and the ability to objectively quantify this finding (as opposed to a clinician grading based on their subjective examination) provides standardization for research. The following technical data is provided by Oculus, Inc.

## Technical Data

### OCULUS Keratograph® 5M

General information	
Measuring range	3 - 38 mm 9 - 99 D
Accuracy	± 0.1 D
Reproducibility	± 0.1 D
Number of rings	22
Working distance	78 - 100 mm
Number of evaluated data points	22 000
Camera	Digital CCD camera
Illumination source	Placido illumination: white diodes Placido illumination: infrared diodes (880 nm) Imaging illumination: blue diodes (465 nm) Meibography: infrared diodes (840 nm) Tear film dynamics: white diodes Pupillometry illumination: infrared diodes (880 nm)
Technical specifications	
Dimensions (WxDxH)	280 x 480 - 505 x 485 - 515 mm (11 x 18.9 - 19.9 x 19.1 - 20.3 in)
Weight	Measuring equipment: 3.2 kg (7.1 lbs) With base and sliding plate: 8 kg (17.6 lbs)
Max. power consumption	18 W
Voltage	90 - 264 VAC
Frequency	47 - 63 Hz
Recommended computer specifications	CPU Intel® Core™ i5-6600, 500 GB HDD, 8 GB memory, Windows® 7 - Windows® 10

 in accordance with Medical Device Directive 93/42/EEC

### 13.0 Risks to Subjects / Evaluating, Monitoring and Reporting Adverse Events / Quality Assurance

This study overall represents a minimal risk to subjects.

Risk with PROSE devices are those that are already associated with wearing any form of contact lens. All contact lens wearers are at risk for developing an abrasion ('cut' on the eye) during lens application or removal as well as inflammatory and/or infectious complications during lens wear, but there is no hypothesized added risk of these occurrences by participating in this study.

Use of RESTASIS does introduce the risk of a hypersensitivity or toxic reaction to an active or inactive ingredient in RESTASIS which could result in corneal or conjunctival irritation, redness, and/or discomfort.

"In clinical trials the most common adverse reaction following the use of RESTASIS® was ocular burning (17%). Other reactions reported in 1% to 5% of patients included conjunctival hyperemia, discharge, epiphora, eye pain, foreign body sensation, pruritus, stinging, and visual disturbance (most often blurring)".

As with any study there may be unanticipated adverse reactions or outcomes.

If a subject experiences an adverse event during the duration of the study, they will be instructed to call the study coordinator who will communicate with the investigators to determine the best course of action. If the subject needs to be seen due to an adverse event, a study investigator will examine them and the customary procedure for management will be followed.

If an adverse event such as an abrasion occurs during a study visit, the condition will be treated as it is customarily, and the fees associated with treatment will be covered by the study.

Any adverse event will be treated and followed in keeping with standard medical and optometric practice. Subjects will be given 24-hour contact information for BostonSight providers and instructions to call if they develop new ocular or visual symptoms while participating in this study. All AEs will be evaluated and managed in an appropriate timeframe at an appropriate facility according to the medical judgment of a BostonSight doctor. All BostonSight patients enrolled in the study will have an ongoing relationship and follow-up with BostonSight for the duration of this study and as long as PROSE devices are being worn.

Any adverse effects or unforeseen events relating to the study will be reported directly to the Principal Investigator and to NEIRB.

Following the conclusion of the study the patient will remain under the care of a BostonSight doctor in the traditional sense, for continued evaluations and management while continuing use of a PROSE device, with financial obligations typical to any BostonSight patient.

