**Visit 2: (1 Week post Restasis dispensing)**

- a. Update past medical history, past ocular history, allergies, medications
- b. Visual acuity assessments of both eyes (logMAR)
- c. Subject's evaluation of symptoms via OSDI
- d. Tolerability questionnaire
- e. Oculus Keratograph 5M R-Scan with lens (automatic classification of redness)
- f. Remove lens
- g. Oculus Keratograph 5M R-Scan without lens (automatic classification of redness)
- h. Slit lamp examination (without lens) including:
  - a. anterior segment and ocular surface
  - b. conjunctival redness (Efron Grading Scale, Modified Efron Grading Scale)
  - c. corneal staining with sodium fluorescein (NEI Grading System)
  - d. conjunctival staining with lissamine green (NEI Grading System)

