**Visit 3: (4 Weeks post Restasis dispensing)**

- a. Update past medical history, past ocular history, allergies, medication
- b. Visual acuity assessments of both eyes (logMAR)
- c. Subject's evaluation of symptoms via OSDI
- d. Tolerability questionnaire
- e. Oculus Keratograph 5M R-Scan with lens (automatic classification of redness)
- f. Remove lens
- g. Oculus Keratograph 5M R-Scan without lens (automatic classification of redness)
- h. Slit lamp examination (without lens) including:
  - a. anterior segment and ocular surface
  - b. conjunctival redness (Efron Grading Scale, Modified Efron Grading Scale)
  - c. corneal staining with sodium fluorescein (NEI Grading System)

d. conjunctival staining with lissamine green (NEI Grading System)

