## 9.0 Study Endpoints

The study endpoints to analyze safety, tolerability and efficacy are as follows:

- a) Visual Acuity (logMAR)
- b) Tolerability questionnaire
- c) Ocular Surface Disease Index (OSDI)
- d) Corneal staining with sodium fluorescein (NEI Grading System)
- e) Conjunctival staining with lissamine green (NEI Grading System)
- f) Conjunctival redness, Efron and modified Efron scale
- g) Oculus Keratograph 5M R-Scan value

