### **Adverse event reporting guidelines:**

All adverse events must be reported in the subject's source documents, and recorded on an Adverse Event Case Report Form regardless of whether or not they are considered to be related to the test article. The recording should be within 24 hours of the time that the AE came to the attention of the Investigator. For non-serious AE it is sufficient to enter the AE information into the CRF. The Clinical Research Coordinator will review the database on a regular basis.

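### Acuity, staining and redness are safety endpoints, but the plan does not require grading them at an unscheduled adverse-event examination and has no rule to bring such values or the adverse-event records into the analysis

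*Protocol*

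**What the plan says.** Protocol section 1.0 makes tolerability and safety the main goal and early efficacy secondary. Section 9.0 opens with "The study endpoints to analyze safety, tolerability and efficacy are as follows" and lists seven measures: acuity, the tolerability questionnaire, OSDI, corneal staining, conjunctival staining, Efron redness and the R-Scan value. Adverse events are not on the list.

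Section 8.0 schedules these measures on drug at Visit 2 (one week after dispensing) and Visit 3 (four weeks after). The statistical paragraph in section 10.0 uses the same two times: "Subjects will be reevaluated at 1 week and 1 month visits and the data will be evaluated and compared to baseline". The SAP adds: "For univariate data analysis (before/after visits), paired t-test was performed". It also names a two-way ANOVA. It has no adverse-event summary and no rule for unscheduled values.

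Section 13.0 tells subjects to call if they have an adverse event. If one has to be seen, "a study investigator will examine them and the customary procedure for management will be followed". Every adverse event is to be "recorded on an Adverse Event Case Report Form regardless of whether or not they are considered to be related to the test article", together with the action taken. Section 15.0 excludes from the analysis the data of any subject who withdraws or is withdrawn, and an adverse event is one stated reason for withdrawal.

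**The concern.** The examination made because something has gone wrong can say more about safety than a scheduled one. In this plan it is the one for which no study grading is required. A subject whose staining or acuity worsens on day 3 and recovers by day 7 can finish the study with acuity, staining and redness values that show no change from baseline. The gap works in one direction, towards apparent safety, and on the study's main question. Ten subjects are analysed (section 5.0), so one such subject is 10% of the sample. A grading not made at the time cannot be reconstructed later.

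**Working it through.** The plan states no figure on this point, so there is none to reproduce. The check has three parts.

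**1. Can an unscheduled grading reach the safety endpoints?**

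- Sections 8.0 and 10.0 describe Visits 1A, 1B, 2 and 3 only. No unscheduled visit or set of assessments is defined.
- Section 13.0 provides for the examination and names no endpoint measure for it. It also leaves the evaluation of adverse events to the judgement of a doctor at the site.
- The reporting rules in section 13.0 ask for the event and the action taken. They do not ask for graded values, but the form is not reproduced, so its fields cannot be checked.
- Section 23.0 and the SAP name tests of differences from baseline. Neither uses adverse-event records or unscheduled values.

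The grading is therefore neither required nor excluded, and if it is made, no rule uses it.

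**2. How often would an episode miss both readings?**

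Inputs from the documents: readings on day 7 and day 28 after dispensing. Assumed, because the documents give neither: an episode of *d* days (*d* at most 7) that resolves without leaving a trace, and one of two onset patterns.

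- Onset uniform over 28 days: present on day 7 with chance *d*/28, and on day 28 with chance *d*/28. The two cannot both occur, so the chance of being seen is 2*d*/28.
- Onset uniform over the first 7 days: present on day 7 with chance *d*/7, and over by day 28.

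| Duration | Seen, onset over 28 days | Missed | Seen, onset in first week | Missed |
|---|---|---|---|---|
| 2 days | 4/28 = 14% | 86% | 2/7 = 29% | 71% |
| 3 days | 6/28 = 21% | 79% | 3/7 = 43% | 57% |
| 5 days | 10/28 = 36% | 64% | 5/7 = 71% | 29% |
| 7 days | 14/28 = 50% | 50% | 7/7 = 100% | 0% |

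An episode seen at a visit is not necessarily seen at its worst.

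These are chances of missing two fixed visits. They are not the loss that a change to section 13.0 could recover. If *e* is the share of missed episodes that lead to an examination while the sign is present, the recoverable share for a 3-day episode is *e* × 57% to *e* × 79%. The documents give no value for *e*.

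**3. Could the worst value on drug simply be tested against baseline?**

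No. With no true change and independent normal reading error, the expected maximum of two readings lies 1/√π = 0.56 SD above the expected single reading. For three readings it is 3/(2√π) = 0.85 SD. On a scale where higher is worse, a scheduled-only subject would appear 0.56 SD worse than a single baseline from noise alone, and a subject with one extra examination 0.85 SD worse. A paired test of worst value against baseline would count this as harm.

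**The case against.** Several stronger readings are tempting, and the documents do not support them.

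- A reader might infer that the examination itself is left to customary care. In the quoted sentence, custom qualifies management, and a study investigator examines.
- A reader might infer that these signs are never graded at such an examination. The protocol is silent, which is not exclusion. An adverse event can also coincide with a scheduled visit ("If an adverse event such as an abrasion occurs during a study visit"), and that visit's schedule includes all the measures.
- A reader might infer that the event is lost to the study. It is not: every adverse event goes into the source documents and onto the form, whether related or not.
- A reader might infer that a subject with a day-3 episode shows no worsening on any safety endpoint. The tolerability questionnaire and OSDI are endpoints too and are completed at Week 1. Their recall periods are not given, so they might pick the episode up.
- A reader might take 79% as the information lost. It depends on the assumed onset, falls to 57% if onset is in the first week, and counts episodes that no examination would have recovered.

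There is also a case for leaving the plan alone. This is a pilot with ten completers whose results are described as mainly observational, and so few adverse-event records can be read one by one. The SAP is written in the past tense, so new gradings may no longer be obtainable. Staining also carries a stated risk of irritation and stinging (section 10.0), here in an eye that already has symptoms.

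These points limit the claim and shape the remedy. They do not remove the gap: neither document requires the grading, and neither plans for the adverse-event records to be read beside the safety endpoints.

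**Conclusion.** The concern holds in a limited form. Acuity, staining and redness serve as safety endpoints with only two on-drug readings. Nothing requires them to be graded at an adverse-event examination between visits, and nothing brings such values or the adverse-event records into the analysis. A sign that worsens and resolves between visits can be absent from these endpoints while the event is on the form.

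The frequency cannot be computed from the documents. The range of 57% to 79% for a 3-day episode rests on the assumed duration and onset, and only the part that leads to an examination is recoverable. For subjects withdrawn because of an adverse event, section 15.0 goes further and removes even their scheduled readings. The point should be addressed: the change is small, and a grading not taken at the time is lost.

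**What to change.** **Protocol section 13.0.** State that at any unscheduled adverse-event examination the investigator also records logMAR acuity, NEI corneal and conjunctival staining and Efron redness on the study worksheet, as far as the eye's condition and clinical judgement allow.

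**SAP.** Add a descriptive safety listing for every subject who received the drug, including those withdrawn, as a stated exception to the exclusion in section 15.0. It shows all adverse events, with any unscheduled gradings beside that subject's baseline and scheduled values. Any worst-on-drug value is descriptive only and is not tested against the single baseline. A note should say that the maximum of several readings is biased towards worsening. The Week 1 and Week 4 efficacy comparisons keep scheduled readings only.

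**If data collection is over.** List the adverse events with whatever gradings are in the source documents, and state as a limitation that these endpoints were read at two time points.

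**Cost.** One worksheet page, a few more minutes at an examination that takes place anyway, and one listing. No visit or instrument is added. The safety table may look less favourable.
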